Mattresses that have dual-functionality are excluded. This may be the ability to switch between static and alternating, such as Talley Quattro or Arjo Duo2; or mattresses that use combined static and alternating functionality, such as Curocell Cirrus or Talley Quattro Fusion. Although these mattresses may have clinical applicability in a community setting, their use during the study could confound results, particularly if they are not used as allocated, for example switched to alternating when the participant has been allocated to the static treatment group.

Cushions

To ensure that changes in pressure injuries are due to the mattress and not impacted by time spent sitting out of bed, all participants will be provided with the same air pressure cushion. Air cushions have been shown to have the lowest interface pressure, along with water cushions (Defloor & Grypdonck, 2000). As there are not many water cushions commercially available, an air cushion will be used (high profile ROHO cushion). These cushions are commonly prescribed for people at high risk of developing pressure injuries and so will be familiar to the treating clinicians should any trouble-shooting be required.

Wound Care

Wound care will be provided to the participants as per the current practice for Community Care Nursing, ACT Health. This includes the use of best-practice methods, such as Mepilex range as wound dressing with foam or cavity fillers as needed. Frequency of wound care days will vary depending on the stage of healing. Generally for Grade 2 wounds, wound care occurs every second day, reducing quickly to twice a week, then once per week. Once the wound reaches the stage of visits once per week the wound is considered almost healed as per the RevPWAT (score <2) and thus endpoint for the study.

Data Collection

Participants will be individually coded to prevent identification by assessors and by primary investigator when collecting survey data. Data will be kept in a limited-access folder on secure ACT Health servers behind ACT Health firewalls.

The methodology will be piloted prior to commencement of the full study to ensure that all components are feasible in practice. From a snapshot taken of the services over a period of 4 months, it is anticipated that intake will be an average of one participant a week so the methodology will be piloted for approximately 8-12 weeks (until endpoint is reached for four participants). It is anticipated that using this same average of intake that data collection for the primary study will take approximately 24 months.

Training of Community Nurses of standardised requirement for taking photographs

To ensure accurate and reliable data is collectable from the photographs a standard operating procedure will be developed. Thompson, et al. (2013) provided tips for ensuring a photograph is taken that is going to reduce the risk of discrepancies between assessors (Information Box 2). In addition to these tips, they also recommend the bedside clinician (ie the person taking the photograph) makes a note of the dressing removed as the dressing type may impact on the surrounding skin or leave residue (Thompson, et al., 2013).

INFORMATION BOX 2: WOUND PHOTOGRAPHY TIPS

- Patient identification number, date and time of when the photograph was taken
- A measurement scale (mm markings preferred) should be placed adjacent to the wound in the same plane as the wound opening.
- Background should be clear of clutter consistent blue or green background is preferred.
- Cleanse, debride and dry the wound area thoroughly before taking photograph
- Use at least a 3.0 megapixel digital camera. Larger than 10 megapixels is not required just results in file storage problems.
- Take photograph close to wound (30-60 cm) and include wound base, all wound edges, sample of periulcer skin (10cm around).
 - Use even consistent, reproducible lighting external ring or extended flash is preferred.
- Avoid shadows and bright spots (open windows, flashlights)
- Take photographs at right angles to the wound opening.
- Stabilise arms or use tripod when taking photograph to avoid shake/movement during photograph.
- Several photographs can be taken at different distances to get "full picture".
- Make notes when taking photographs so subsequent photographs are taken in the same orientation.
- Prevent camera cross contamination follow aseptic technique and disinfection procedure.
- Ensure informed consent is obtained for defined use (time frame and purpose) of photographs.
- Patient's privacy should be respected at all times use drapes to obscure the view of body parts not involved with the wound.
 - Develop a consistent file labelling system and a secure back-up system with ample storage space.
 - Store de-identified photos in a secure location and develop or follow relevant site policies and procedures to ensure patient confidentiality is maintained.

Data Analysis

Sample size

Power calculations were unable to be completed due to unavailable data regarding standard deviations (SD) in previous literature. Articles reviewed either did not utilise similar outcome measures or did not report the SD due to non-normal distributions. A priori sample was determined for a total sample of n=80 to aim for a minimum final total sample of n=60 (to allow n=30 for each group, utilising the central limit theorem

(Field, 2013)) after allowing for withdrawals. Power calculations, including Cohen's d for effect size, will need to be completed at the completion of data collection.

Test inter-rater reliability of assessors of photographs

Although Thompson, et al. (2013) describe the inter-rater reliability of the RevPWAT, it is important to ensure the inter-rater reliability of the assessors with this wound type. Thompson, et al. (2013) tested reliability using a range of wound types that included pressure injuries however also had strict guidelines regarding the wounds at baseline to ensure good photographs were able to be taken, such as circumferential wounds (Thompson, et al., 2013). Photographs from the pilot study will be used to test inter-rater reliability of assessors.

Statistical Analysis

As the study has a non-inferiority design, data analysis will be completed twice and compared: one a Per Protocol analysis and one an Intention to Treat analysis. This is because each type of analysis biases different treatment groups (Scott, 2009) so by comparing the two analyses the results will be crossvalidated. For a similar reason, analysis will look at p-values of the relevant statistical tests as well as confidence intervals (where the confidence interval falling outside the pre-determined effect size will indicate equivalence or non-inferiority)(Greene, Morland, Durkalski, & Frueh, 2008).

Provided the relevant assumptions have been met, the following statistical tests will be completed:

Outcome Measure	Statistical Test			
Comparing wound healing times	Independent t-test (average healing time reactive surfaces vs average healing time active surfaces)			
Comparing number of new pressure injuries developed	Independent t-test (total number of new pressure injuries reactive surfaces vs total number of new pressure injuries active surfaces)			
Comparing number of pressure injuries not healed at 8 weeks	Independent t-test (number of pressure injuries not healed at 8 weeks for reactive surfaces vs active surfaces)			
Changes in Pain scores	2-way Mixed ANOVA – between group analysis to compare pre- and post-pain scores for each mattress type, independent group analysis to compare the mattress types			
Changes in time spent in bed	2-way Mixed ANOVA – between group analysis to compare pre- and post-time for each mattress type, independent group analysis to compare the mattress types			
Changes in frequency of repositioning	2-way Mixed ANOVA – between group analysis to compare pre- and post-frequencies for each mattress type, independent group analysis to compare the mattress types			

If the assumptions cannot be met, despite data transformation, then the relevant non-parametric tests will be completed (eg Mann-Whitney instead of Independent t-test).

Ethical Considerations

Ethics Approval

Ethics approval for this study will be sought from the ACT Health Human Research Ethics Committee and the University of Canberra Human Research Ethics Committee. As the design of the study reflects current practice, with all chosen mattresses being supplier-stated to be appropriate for Grade 2 pressure injuries, there will be minimal risk to participants for participating.

Data Management

During the data collection phase, data will be kept in restricted folders on ACT Health servers behind ACT Health firewalls so that all required parties will be able to access the data, negating the need for data to be emailed or transferred via USB. At the completion of the project the data will be de-identified and a copy provided to University of Canberra for archiving. This record is expected to be maintained for a minimum of seven years as per ACT Legislative requirements ("Health Records (Privacy and Access) Act 1997 (Republication No 27) (ACT)," 2016). Clinicians will continue to document in the clinical file as per current policy, including the allocated mattress.

Consent and cognitive impairment

It is likely that through coincidence there will be participants who do not have capacity to consent to participate. Potential participants will be screened for cognitive impairment and flagged for additional investigation via a cognitive screening assessment. This study is considered by ACT Legislation as 'low risk research' due to the fact it is comparing the effectiveness of two established standard treatments during routine health care (ACT Health Research Ethics and Governance Office, no date). As a result, if a cognitive impairment is determined then consent will be sought from the potential participant's (in priority order):

- person with enduring power of attorney;
- their guardian; or
- their health attorney, defined as a domestic partner, their carer or a close relative or friend (ACT Health Research Ethics and Governance Office, no date).

This is the most likely vulnerable population to be included in the study.

Adverse Event - Deterioration or development of new pressure injuries

All new pressure injuries and all deteriorating pressure injuries will be referred to the Data Safety and Monitoring Board (DSMB), consisting of Community Care Wound CNC, Community Care Wound Nurse Practitioner and Primary Investigator. This committee will review the circumstance to determine the cause of the deterioration or new pressure injury. If the suspected cause is something external to the mattress then the mattress may be able to remain in place. If no external cause can be found, then it is possible the mattress may have been a factor and the participant may need to leave the trial. This will also be the case should the pressure injury deteriorate to become a Stage 3, Stage 4, Suspected Deep Tissue Injury or Unstageable pressure injury.

Support surface provision during the study

Support surfaces being provided for the study are being supplied by one of two options:

- Equipment suppliers Astris Lifecare and Invacare (mattresses and cushions are being donated for the duration of the study, provided on a needs-basis).
- ACT Health Equipment Loan Service

Which service provides the support surfaces will depend on availability at the time and speed that delivery can occur. Agreements are being drawn up with Astris Lifecare and Invacare with regards to maintaining the privacy of participants and the intellectual property of the results, including the agreement that the results

will be published, regardless of the outcome. ACT Health equipment will only be utilised for participants who would normally be accessing this equipment, as per current practice.

Support surface provision at the end of the study

As a large number of people with a pressure injury are likely to need pressure care on a long term basis, systems need to be in place to aid the long term provision once the study has completed. At the intake of the study, participants will be receiving an initial occupational therapy assessment which will anticipate any long term equipment needs and refer on appropriately. This initial assessment will be handed over to the treating occupational therapist for follow up at the completion of the study.

Study protocol audits

The DSMB will be responsible for the completion of a quarterly audit to ensure adherence to the protocol is maintained. This will involve checking consent forms have been obtained, photograph documents and assessment documents are saved in the appropriate places and that surveys and mattress provision within the allocated timeframes.

Project Plan

Date	Activity		
Nov 2017 – Jan 2018	HREC Approval sought (ACT Health and UC)		
	Training of Community Nurses for team participating in Pilot		
Feb – Apr 2018	Pilot Study to test methodology		
Apr – Jun 2018	Review results of Pilot Study regarding methodology and data collection – proposed		
	changes to methodology submitted to HREC for approval		
Apr – Jun 2018	Training of Community Nurses for remaining participating teams		
Jul 2018 – Jul 2020	Primary data collection phase – data collection expected to take approx 18-20		
	months with an average of one participants enrolled each week (based on snapshot		
	of potentially eligible participants from Aug-Dec 2016)		
Jul 2020 – Jul 2021	Data analysis		
Jul 2021 -	Writing results, including publications and thesis		

Research Outcomes

Primary Publication	PhD Thesis			
Proposed Journal	Literature review			
Publications	Pilot study			
	Primary RCT focusing primarily on the wound healing component with subjective factors as supportive			
	Article focusing in more detail on the survey results and subjective factors of the mattresses			
Conference Papers	Literature review			
	Results regarding Pilot Study			
	Results regarding Primary RCT			
	would include Occupational Therapy conferences, Wound Care conferences, Nursing Technology conferences			

Budget and Resources Required

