Clinical guidelines recommend management of the extrinsic factors to reduce incidence and to treat existing pressure injuries (NPUAP, EPUAP, & PPPIA, 2014). One of the key strategies is the provision of appropriate support surfaces, such as pressure mattresses and pressure cushions (NPUAP, EPUAP, & PPPIA, 2014). There is a wide range of support surfaces available with differing techniques for providing pressure care. Reactive surfaces use envelopment and immersion to increase surface area, reducing interface pressure. Active surfaces use removal of pressure for short periods of time to allow improved re-perfusion. When prescribing an appropriate mattress the clinician needs to take into consideration a range of factors: the individual's pressure injury risk level as determined with risk assessment tools in conjunction with clinical reasoning, the individual's ability to move and reposition off the at risk area, their risk factors and the environment the support surface will be used (NPUAP, EPUAP, & PPPIA, 2014).

Often clinicians are reliant on supplier-stated claims of the degree of pressure care to prescribe mattresses with active support surfaces considered a higher level of pressure care than reactive, and thicker support surfaces also being seen as providing a higher level of pressure care. However technological advances have seen an increase in reactive mattresses that are supplier-stated to provide a comparable level of pressure care to active surfaces, with the added benefit of being easier to reposition on.

The research that has been completed to date in the area of pressure care mattresses has been lacking in quality with significant methodological limitations such as lack of blind assessors, underpowered and presence of confounding factors (Chou et al., 2013; McInnes, Dumville, Jammali-Blasi, & Bell-Syer, 2011; McInnes et al., 2015). The better quality studies have not found any statistically significant differences however as they have generally focused on mattress brands rather than the over-arching mattress types they are less transferable into other clinical settings, particularly as the studies age and technological advances occur.

Definitions

Pressure injury grading

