Q: What is the comparative effectiveness of active and reactive pressure mattresses with regards to pressure injury healing for people aged 65 years or older living in the community?

Given the limitations identified in the available literature, the research aim is to compare the effectiveness of the two main types of pressure mattress commonly prescribed for clients over 65 years in a community setting. It is hypothesised that additional issues regarding mattress use in a community setting are likely to arise due to less familiarity with the equipment and less availability of support for pressure care.

As the primary focus is the measured effectiveness, a quantitative approach will be taken utilising a randomised-controlled trial (RCT) methodology. A RCT will eliminate biases such as selection bias and will monitor and control for many of the confounding variables by having a high likelihood of being representative of the population. Although current literature has had methodological limitations, trends indicate that the two mattress types are equivalent or, at a minimum, non-inferior. As a result, the analysis and hypotheses will reflect an equivalency RCT with the methodology represented in Diagram 2. A pilot study is also planned to test the methodology prior to commencement of the main study.

[figure not shown]

Diagram 2: Proposed Treatment Flowchart

 ${\sf RevPWAT-Revised\ Photographic\ Wound\ Assessment\ Tool}$

Equivalency RCT Hypotheses

Primary Outcome (Wound healing times)

Ho: One mattress type is clinically more effective at improving wound healing times for pressure injuries Ha: The type of pressure mattress provided makes no difference on wound healing times for pressure injuries

Secondary Outcome (Subjective factors of mattress acceptability)

Ho: One mattress type is easier to use and more acceptable to use

Ha: Both mattress types are equally easy to use and equally acceptable

Recruitment

All incoming referrals to ACT Health Community Care Nursing or Community Care Occupational Therapy will be compared against the inclusion and exclusion criteria.

Inclusion Criteria

- 1. aged 65 years or older elderly people are more prone to development of pressure injuries due to reduce skin elasticity and connective tissue and increased number of health complications, which in turn impacts on the extrinsic and intrinsic risk factors (Lake, 2015; Palese et al., 2015).
- 2. residing in a community setting ie in a private home

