The Revised Photographic Wound Assessment Tool (RevPWAT) is an assessment tool based on the Bates-Jensen Wound Assessment Tool (formerly known as the Pressure Sore Status Tool) for assessments based on photographs of wounds rather than bedside assessments (Thompson, et al., 2013). This outcome measure has been chosen as it does not require the assessors to be at the bedside of the participants, thus blinding them from the allocated mattresses. Blinding assessors from allocated mattresses has been problematic for many of the studies in the literature as the mattresses have visible differences. Thompson, et al. (2013) tested the RevPWAT for reliability and found a strong correlation between bedside assessments and assessments from photographs (intraclass correlation coefficient of 0.89). See Appendices A and B for the assessment tool and instructions on how to score it.

DELIVERY AND FREQUENCY: Photographs for this assessment tool will be taken by clinicians at each wound care session to measure the progression of wound healing and will be scored by assessors blinded to allocated treatment group.

Secondary - Subjective Factors of Pressure Mattresses

Research has shown that there is a strong correlation between non-use of assistive technology and user dissatisfaction, with some of the factors relating to comfort and ease of use (Federici & Borsci, 2011). Regarding pressure mattresses, this means that equipment abandonment will be more likely if the client does not find the mattress comfortable or struggles with moving on it. These subjective measures are considered just as important as wound healing time and so will be measured through surveys provided approximately one week after mattress provision, utilising a Likert scale. The following factors will be included in the survey:

- participants' perceptions of the allocated mattress positives and negatives
- perceived change in sleep habits including:
 - time spent in bed
 - frequency of repositioning
 - sleep position
- comfort of the mattress, including changes in pain levels (see Pain Scale below)
- ease of transfers
- ease of use, including any troubleshooting they have needed to do to date

DELIVERY AND FREQUENCY: This survey will be completed at baseline and then again approximately 1-2 weeks after mattress provision. It will be completed by the participants and facilitated by the primary researcher.

Secondary - Pain Scale using 10-point Scale (Richards, 2015)

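### The secondary hypotheses tie ease of use and acceptability together so that Ho and Ha are not complementary, and the difference tests listed for the survey outcomes cannot establish Ha

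*Protocol*

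**What the plan says.** Under Research Question and Design, the protocol states that "the analysis and hypotheses will reflect an equivalency RCT", because "trends indicate that the two mattress types are equivalent or, at a minimum, non-inferior". The next section, Equivalency RCT Hypotheses, applies this form to both outcomes. For the secondary outcome, subjective factors of mattress acceptability, the pair is:

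- "Ho: One mattress type is easier to use and more acceptable to use"
- "Ha: Both mattress types are equally easy to use and equally acceptable"

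The Outcome Measures section gives these factors high standing: "These subjective measures are considered just as important as wound healing time". The reason given is that "equipment abandonment will be more likely if the client does not find the mattress comfortable or struggles with moving on it". It lists comfort, ease of transfers and ease of use as separate survey items.

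The Statistical Analysis section plans p-values together with confidence intervals, the latter compared with an effect size that it calls pre-determined but does not give. Its table lists a two-way mixed ANOVA for each of three survey outcomes: pain, time spent in bed and frequency of repositioning. The stated fallback, if assumptions fail, is a non-parametric test.

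**The concern.** A hypothesis pair is useful only if rejecting Ho leaves Ha as what remains. Here Ho requires one type to win on both attributes, and Ha requires a tie on both. Mixed results belong to neither.

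Mixed results are plausible. Comfort, ease of transfers and ease of use are different things and can diverge. The protocol's own evidence table also shows that similar clinical results need not bring similar acceptability. In the large trial of alternating replacements against alternating overlays, incidence (p=0.75) and time to healing (p=0.86) did not differ, but more overlay participants asked for a change because of dissatisfaction (23.3% against 18.9%, p=0.02). That trial compared active surfaces with each other, and another trial in the table, static against dynamic, found no difference in comfort. So this evidence does not predict the present result. It shows only that the equivalence form needs its own justification when carried over to subjective outcomes.

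At stake is what may validly be said about ease and acceptability. If healing turns out similar, these outcomes would naturally inform the choice between types.

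**Working it through.** **1. Do Ho and Ha cover the possibilities?** The inputs are the two hypotheses as worded. Call the types A and B. On each attribute the truth is 'A better', 'equal' or 'B better', which gives 3 × 3 = 9 joint states. (If a margin were set, 'equal' would mean within the margin, and the count would not change.)

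| Ease of use | Acceptability: A better | Equal | B better |
|---|---|---|---|
| A better | Ho | neither | neither |
| Equal | neither | Ha | neither |
| B better | neither | neither | Ho |

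- Ho: 2 states. Ha: 1 state. Neither: 9 − 2 − 1 = 6 states.
- Of the six, 2 are trade-offs (easier but less acceptable) and 4 are better on one attribute and equal on the other.
- Ho is false in 9 − 2 = 7 states, and Ha is true in only 1 of those 7.

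These are counts of logical states, not probabilities.

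**2. Do the listed tests address Ha?** Ha asserts equality. A mixed ANOVA takes no difference as its null, so a significant result speaks against equality and a non-significant one leaves the question open. Neither outcome establishes Ha.

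**3. How weak is non-significance as evidence of equality?** The protocol gives no SD, power, alpha or margin value, so there is no figure to reproduce. Its target is n=80 enrolled for n=60 analysed, 30 per group (allowed loss 1 − 60/80 = 25%). The illustration below assumes a simple two-group comparison in SD units and a normal approximation.

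SE = √(2/30) = 0.258.

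Power of a two-sided 5% difference test = Φ(d/SE − 1.96):

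| True difference d | Power | Chance of non-significance |
|---|---|---|
| 0.3 SD | 21% | 79% |
| 0.5 SD | 49% | 51% |
| 0.8 SD | 87% | 13% |
| 1.0 SD | 97% | 3% |

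The difference detectable with 80% power is (1.96 + 0.84) × 0.258 ≈ 0.72 SD.

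**4. What would a claim of equality need?** With two one-sided tests at 5% each and a true difference of zero, power = 2Φ(m/SE − 1.645) − 1 for margin m, or zero if m/SE is below 1.645:

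| Margin m | Power, 5% per side | Power, 2.5% per side |
|---|---|---|
| 0.3 SD | 0% | 0% |
| 0.5 SD | 23% | 0% |
| 0.8 SD | 85% | 75% |
| 1.0 SD | 97% | 94% |

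At this size, equality could be shown reliably only against a wide margin.

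**The case against.** The strongest reply is that this is loose drafting in a secondary outcome, which the Research Outcomes table treats as supportive in the main paper. A difference in the null is what any equivalence design has. The survey items are separate and no joint test is described. If each item's confidence interval were judged against a sensible margin, a trade-off would ordinarily fail equivalence on both items, so equal ease and acceptability would not be declared. How the survey items are analysed may also be settled in a statistical analysis plan.

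Most of this stands, and it rules out several stronger conclusions that a reader might draw.

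- **That the protocol expects reactive mattresses to be easier to move on.** The Introduction does say "with the added benefit of being easier to reposition on", but as background, in a sentence about mattresses "supplier-stated to provide a comparable level of pressure care to active surfaces". The Conclusion of the literature review calls supplier-stated claims unreliable. No hypothesis predicts this result.
- **That a real difference could never be concluded.** It is not the formal alternative, but the planned confidence intervals and ANOVAs, one of them on repositioning, could still show it.
- **That either verdict would be wrong under a trade-off.** Not rejecting Ho does not assert Ho, so it is not a false verdict.
- **That a trade-off would be reported as equality.** No described procedure does this.

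What the reply does not remove is that the stated pair is non-complementary as worded, and that the tests the protocol itself lists for survey outcomes run in the opposite direction from the stated Ha. A later analysis plan can define tests, but it would inherit hypotheses that still need correcting.

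**Conclusion.** The point holds as a correction to wording and to the match between hypotheses and tests. Six of nine joint states satisfy neither secondary hypothesis, so rejecting Ho does not support Ha. Nor can the difference tests listed for pain, time in bed and repositioning frequency. This part rests on the protocol's words alone.

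The power figures are illustrative only. They assume 30 analysed per group, 5% two-sided tests (or 5% or 2.5% per side for equivalence), standardised differences and a simple two-group comparison. They show how often non-significance would arise despite a real difference, not that the trial is wrongly sized.

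Using an equivalence form for a secondary outcome is not in itself an error. The correction should be made because it governs what may be claimed on outcomes that the protocol ranks with healing time.

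**What to change.** Replace the single secondary pair by one pair per attribute: ease of use and transfers, comfort, and acceptability. State each in the form the planned tests address: Ho, no difference between mattress types; Ha, the types differ; two-sided. Report each estimate with its 95% CI, and state that a non-significant result will not be read as equality.

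If equivalence is truly intended for an attribute, state it for that attribute alone with its own margin (Ho, the absolute difference is at least the margin; Ha, it is smaller). Judge it by whether the confidence interval lies within the margin. The Statistical Analysis section now describes an interval falling outside the effect size, so that sentence should be aligned.

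Either route leaves no outcome unassigned for any attribute. The cost is protocol wording, with no new data or participants. The downside is that the blanket claim of equal ease and acceptability is given up unless margins are set, though the listed tests could not have supported it.

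### Power and Cohen's d are deferred until the data are in, while the equivalence verdict rests on a predetermined effect size that the protocol never states

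*Protocol*

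**What the plan says.** All references are to the protocol.

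- **Data Analysis, Sample size.** No planning calculation was made: "Power calculations were unable to be completed due to unavailable data regarding standard deviations (SD) in previous literature". The target is 80 enrolled to leave at least 60, or 30 per group, justified by the central limit theorem. Power calculations, including Cohen's "d for effect size, will need to be completed at the completion of data collection".
- **Data Analysis, Statistical Analysis.** The plan is that "analysis will look at p-values of the relevant statistical tests as well as confidence intervals", with the decision rule "where the confidence interval falling outside the pre-determined effect size will indicate equivalence or non-inferiority". The planned test of healing time is an independent t-test.
- **Research Question and Design.** The protocol states that "the analysis and hypotheses will reflect an equivalency RCT", whereas Statistical Analysis begins "As the study has a non-inferiority design, data analysis will be completed twice and compared". The hypotheses speak of one mattress type being clinically more effective, without saying how large a difference would count.
- **Project Plan.** The April to June 2018 row reads "Review results of Pilot Study regarding methodology and data collection" and provides for methodology changes to go to the ethics committee. Main data collection starts in July 2018.

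**The concern.** An equivalence or non-inferiority claim is only as good as the bound it is judged against, and that bound must be fixed before the result is seen. Here it is called predetermined but never given, and the one effect-size calculation the protocol describes is scheduled for after data collection. Someone following the document as written would reach the end of the trial with the interval in hand and the bound still open. A positive verdict could then be criticised as fitted to the interval, and so could a negative one.

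The second problem is the deferred power figure. Power evaluated at the observed effect carries no information beyond the p-value. For a test of difference it is smallest when the observed difference is near zero, which is the result that best supports equivalence.

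**Working it through.** **The plan's own figures.** No power, significance level, SD or margin is stated, so there is no power figure to reproduce. The only arithmetic that can be checked is 2 × 30 = 60 and 60 / (1 − 0.25) = 80. The 25% loss is implied by the 60 and 80, not stated.

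**Where the bound is fixed.** Three places bear on it:

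| Place | What it gives |
|---|---|
| Equivalency RCT Hypotheses | no difference in days, SD units or as a ratio |
| Sample size | Cohen's d, after data collection |
| Statistical Analysis | an effect size called predetermined, with no value, scale or date |

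The text points to no other place where the bound is held.

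**Observed power of the planned t-test.** Inputs: 30 per group (protocol), two-sided 5% (assumed, since the protocol states no level), df = 58, critical t = 2.00. The standard error in SD units is √(2/30) = 0.258. For an observed standardised difference d, t = d / 0.258. Observed power is the probability that a noncentral t with 58 df and noncentrality t exceeds 2.00 in absolute value.

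| p-value | Observed power |
|---|---|
| 0.90 | 5% |
| 0.50 | 10% |
| 0.20 | 25% |
| 0.05 | 50% |

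Read from d instead: d = 0 gives p = 1.00 and 5%; d = 0.2 gives p = 0.44 and 12%; d = 0.5 gives p = 0.058 and 48%; d = 0.8 gives p = 0.003 and 86%. At a given sample size the power figure is a function of the p-value alone, and it rises as the arms move apart.

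**How this looks in a trial where equivalence is true.** Simulation with true difference 0, 30 per group, two one-sided tests (TOST) through a 90% interval, and a margin of 0.8 SD. The margin and interval level are illustrative, not the protocol's. About 84% of trials establish equivalence. Among those the median observed power is about 8.5% and none reaches 80%. Among trials that fail to establish equivalence the median is about 40%.

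**The alternative reading: TOST power.** With margin m, true difference d and 5% per side, power ≈ Φ((m − d)/0.258 − 1.645) + Φ((m + d)/0.258 − 1.645) − 1, with negative values set to 0. At m = 0.8 this gives 85% at d = 0, 61% at d = 0.3, 31% at d = 0.5 and 5% at d = 0.8. This runs in the sensible direction, but evaluated at the observed d it is still only another expression of the result.

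**What 30 per group could support.** With true difference 0 and 80% power, the smallest margin under TOST is (1.645 + 1.282) × 0.258 = 0.76 SD at 5% per side, or (1.960 + 1.282) × 0.258 = 0.84 SD at 2.5% per side. At an assumed margin of 0.5 SD and 5% per side, power with 30 per group is 23%, and 80% power needs 2 × ((1.645 + 1.282)/0.5)² = 69 per group after rounding up.

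**The case against.** The strongest defence is that the protocol describes two separate things: a bound set beforehand but not quoted in this document, and a descriptive d computed at the end as part of a deferred power calculation. A reader might infer that the post-data d will itself serve as the bound. The documents do not say so, and the word predetermined points the other way. Consequences that need that link, such as a bound that widens in days as the trial's own scatter grows, or one the interval could never lie within because it is centred on d, are therefore not findings against this protocol. What survives is narrower: the bound is relied on but not stated, and the only described effect-size step comes too late to supply it.

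Secondly, the protocol names no test for the deferred power and does not say it will be evaluated at the observed difference. Since missing SDs are the reason for deferral, the intention may be to put the trial's SD into a power calculation for the bound. This is fair. The backwards behaviour holds only for observed power of a difference test. The planned t-test makes that reading plausible, not certain.

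Thirdly, one might infer that trials supporting equivalence would be declared underpowered. No rule in the protocol says so, and post-hoc power has no role in the verdict, which rests on intervals and p-values in both analysis populations. The harm from the power figure is to interpretation, not to the decision rule.

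Finally, the 5% level, the 90% interval and the 0.8 SD margin are assumptions. The link between p-value and observed power needs the level and group size but no margin.

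**Conclusion.** The point holds in this limited form. The protocol places power and Cohen's d after data collection and judges equivalence or non-inferiority against an effect size it never gives, so the bound is open to being chosen when the interval is known. This is more than detail left to an analysis plan, because the protocol itself schedules its only effect-size step after the data while calling the bound predetermined. It is not established that d will be the bound.

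The power figure is uninformative on either reading. If it is the observed power of the t-test, it is also misleading for an equivalence aim: 5% when p = 0.90 and 50% when p = 0.05, with 30 per group and a two-sided 5% level.

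**What to change.** 1. Delete the sentence that puts power and Cohen's d at the end of data collection.
2. State a clinically justified bound on the healing-time scale, in days or as a ratio of healing rates, with its confidence level. Do not express it in SD units of the trial's own data. Date it before the first main-study participant; the April to June 2018 ethics submission is a natural place.
3. Report the confidence interval against that bound, with no observed power.
4. If a planning check is wanted, use the pooled SD or event count, blind to arm. The pilot runs only until four participants reach endpoint, so its SD would be very imprecise. A bound in days needs no SD.

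The cost is a short amendment. The change itself does not require enrolling more patients, but once a bound is fixed the planned 30 per group may turn out to have limited power for it (23% at an illustrative 0.5 SD). That should be stated openly in the protocol and in the report.
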